Accordingly, the central hypothesis of this translational human pilot project, and a more definitive project based on it, is as follows: PD is a human anxiety disorder associated with specific cortical and subcortical GABA deficits that result in disruption of normal inhibitory regulation of pro-arousal ORX neurons. This disruption promotes excessive ORX release, sympathetic activation,¹³ and vulnerability to spontaneous or chemically induced panic. Pretreatment with an ORX1 receptor antagonist^{14,15} prior to chemical challenge, as proposed in this submission, is therefore expected to block the evoked panic response.

Rationale for the Use of CO₂ Inhalation

The 35% CO₂ challenge is well documented in the literature as being reliable, safe, and easy to administer.^{16,17} The procedure has acceptable test-retest reliability,¹⁸ and may be used to monitor improvement in clinical status following the administration of antipanic medications.¹⁹

Approximately 70% of PD patients will have a panic attack in response to this challenge, which closely resembles a real-life panic.²⁰ Therefore, in addition to resting/baseline measurement of plasma ORX A, we also will examine CO₂-evoked levels of plasma ORX A in PD patients, and we will correlate these responses with other behavioral and physiological parameters recorded during the CO₂ test. The PI has had considerable experience using PD challenge paradigms in clinical research contexts, and he is very familiar with the application of the 35% CO₂ challenge.^{21,22}

PROJECT AIMS AND EXPECTED RESULTS

The project is a 1-year study that gathers pilot data relating to the role of orexin in human panic disorder. The effect sizes generated from this pilot work will permit planning and powering of a larger-scale study. It is anticipated that we will complete the study over the course of one year.

Specific Aim 1 will be to provide a preliminary demonstration that acute administration of the first-in-class, FDA-approved insomnia agent, suvorexant,^{14,23} a mixed ORX1/2 receptor antagonist, will block 35% CO₂-induced panic symptoms in panic disorder (PD) patients, via amelioration of central ORX neuronal hyperactivity (as reflected in blunted plasma ORX responses to CO₂ challenge).

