The PI or sub-I will be present when the subject takes the study drug or placebo (-120 minutes; see Table 3). At that time, and until the CO₂ inhalation test is about to begin (-120 mins to 0 mins), the Research Coordinator will be present in the room. From the time of the CO₂ inhalation test (0 mins) until the patient leaves accompanied by a friend or family member (+60 mins), both the Research Coordinator and the PI or sub-I will be present in the room.

-130 mins	Patient welcomed to the CRC. Taken to the testing room. Baseline behavioral ratings and vital signs obtained. 7 cc blood drawn (ORX)	PDSS, CGI-S; Vital Signs (VS); ORX
-120mins	Administer single oral dose of suvorexant 10 mg or identical-appearing placebo with water.	
-10 mins	Obtain pre-CO ₂ test baseline behavioral and physiological (vitals) measures.	VAS (5 items), PSS; VS

-5 mins	Plastic mask attached, and patients on room air for 5 minutes. 7cc blood drawn (ORX)	ORX level
0 mins	Blindly switch to 35% CO ₂ / 65% O ₂ gas mixture inhalation for 60 seconds.	
+1 mins	Monitoring for panic/anxiety symptoms, ORX	VAS, PSS, VS, ORX
+5 mins	Monitoring for panic/anxiety symptoms	VAS, PSS, VS
+15 mins	Monitoring for panic/anxiety symptoms, ORX	VAS, PSS, ORX, VS
+30 mins	7 cc blood drawn (ORX)	ORX
+60 mins	Monitoring for panic/anxiety symptoms. If patient stable discharge from the CRC, accompanied by a family member, friend, or caregiver.	VAS, PSS VS

ORX and DNA blood samples: Blood samples for ORX ELISA analysis will be collected, prepared and processed by the study coordinators. The samples will be collected into 7 ml Vacutainer tubes (#VT-6450) which contain EDTA (lavender top). The tubes will be shaken gently several times immediately after collection to promote anti-coagulation. Blood will then be transferred to centrifuge tubes and centrifuged at 1,000 x g for 15 minutes at 4°C. 1 mL plasma samples will be removed, and stored in a -80°C freezer located in the CRC.⁴⁷ From those subjects who have provided their (additional informed consent to allow a blood sample to be collected for future DNA analysis, a sample of this centrifuged blood (after the plasma has been removed) will be banked in a -80°C freezer located in the CRC for future candidate gene/DNA analysis. Genes of interest with respect to ORX metabolism are the preproORX gene and genes that code for the receptors, ORX1 and ORX2.

Suvorexant/Placebo Medication, and Rescue Medication

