All data analyses will be performed using SPSS version 22. Continuous variables will be summarized separately in the two PD patient groups using descriptive statistics, including mean, SD, minimum and maximum values. Categorical variables (e.g., presence/absence of a CO₂-panic episode) will be summarized using frequency counts and percentages. Baseline demographic data will be compared between the two groups. Dichotomous and ordinal variables will be examined using Fisher's exact tests, and continuous measures (e.g., peak change from baseline in CO₂-evoked VAS anxiety, and peak change from baseline in plasma ORX) with Wilcoxon rank sum tests. Effect sizes will be generated to facilitate planning of a definitive study.

Since our current pilot data (see p. 3) are so limited, the data generated through this study will enable us to estimate power requirements for a larger study, and to fine-tune the protocol. A speculative power estimate for the larger study, based on our current plasma ORX/CO₂ findings, is as follows:

If we assume a mean \pm SD peak change value of 50 \pm 25 pg/ml for the PD/placebo group, and 30 \pm 25 pg/ml for the PD/suvorexant group, we would have 80% power to detect this difference, with $\alpha=0.05$, utilizing a 2-tailed Students t-test, with 25 patients in each group.

The pilot study timeline will be as follows: 3 months to start up and obtain IRB approval; an 8-month enrollment period, recruiting 1-2 patients per month; and a final month for analysis, poster development, and development of a grant application to fund a definitive study of the research questions being addressed by this pilot work.

References

1. de Lecea L, Sutcliffe JG. The hypocretins/orexins: Novel hypothalamic neuropeptides involved in different physiological systems. *Cell Mol Life Sci.* 1999;56(5-6):473-480.
2. Sakurai T. The neural circuit of orexin (hypocretin): Maintaining sleep and wakefulness. *Nat Rev Neurosci.* 2007;8(3):171-181.
4. Samson WK, et al. Both type 1 and type 2 receptors transmit the behavioral effects of orexin/hypocretin. *The FASEB Journal.* 2007;21(5):A462.

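### Should the plasma orexin comparison be adjusted for the pre-dose orexin value?

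*Combined protocol and SAP*

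**What the plan says.** Data Management and Statistical Considerations assigns continuous measures, including "peak change from baseline in plasma ORX) with Wilcoxon rank sum tests". It names no covariate and no model. It also promises group means and SDs, and adds: "Effect sizes will be generated to facilitate planning of a definitive study". Project Aims and Expected Results gives the same purpose: "The effect sizes generated from this pilot work will permit planning and powering of a larger-scale study".

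Table 3 has two ORX draws before the gas is given:

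- At −130 min, 10 minutes before the capsule: "Baseline behavioral ratings and vital signs obtained. 7 cc blood drawn (ORX".
- At −5 min, 115 minutes after the capsule: "Plastic mask attached, and patients on room air for 5 minutes. 7cc blood drawn (ORX".

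The statistical section does not say which of these is the baseline of the change score. The larger study is sized on peak change of 50 against 30 pg/ml, SD 25 in each arm, for 80% power, "utilizing a 2-tailed Students t-test, with 25 patients in each group".

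**The concern.** Three features together suggest a missed opportunity.

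- The pilot exists to produce planning figures, and a rank-sum test by itself yields no adjusted difference, residual SD or baseline correlation.
- The −130 min sample precedes dosing, so treatment cannot affect it. It is a legitimate covariate that costs nothing extra to collect.
- Analysis of covariance (ANCOVA) with a prognostic baseline usually gains precision in a randomised trial, and with 12 patients any gain would be welcome.

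If the gain were real and dependable, the plan would be passing on a noisier effect size than its data allow, and the larger study might be sized too high.

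The word baseline adds to the unease. Rationale for the Use of CO₂ Inhalation speaks of evoked levels "in addition to resting/baseline measurement of plasma ORX A", and Table 3 uses the word at −130 min and again at −10 min: "test baseline behavioral and physiological (vitals) measures". Change from −130 min would include any drug effect on resting ORX; change from −5 min would isolate the response to CO₂.

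**Working it through.** **Inputs from the protocol.** 6 patients per arm; SD of peak change 25 pg/ml; difference 50 − 30 = 20 pg/ml; two-sided α 0.05; power 80%; 25 per group in the larger study.

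**Inputs that must be assumed.** The correlations among the ORX samples and the ratio k of peak SD to baseline SD. The documents give neither.

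**The plan's own figure.** The normal approximation gives 2 × (1.96 + 0.8416)² × 25² / 20² = 24.5, so 25 per group, as stated. The exact t calculation gives 25.5, so 26, with 79.1% power at 25. The stated figure reproduces, and its inputs are group means and SDs of peak change, which the plan will report.

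**Cost and gain of adjustment at 6 per arm.** Relative to the unadjusted change, the expected variance is

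(1 − ρ²) × (1 + 1/(2n − 4)) = 1.125 × (1 − ρ²) for n = 6.

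The residual degrees of freedom fall from 10 to 9, so the 95% interval width is multiplied by (2.262/2.228) × √[1.125 × (1 − ρ²)] = 1.015 × √(variance ratio). Break-even is |ρ| = 0.33 for variance and 0.37 for width.

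The unadjusted half-width is 2.228 × 25 × √(2/6) = 32.2 pg/ml.

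**Scenarios, change from −130 min.** Here ρ = (rk − 1)/√(k² + 1 − 2rk), with r the baseline–peak correlation.

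| k | r | ρ | Variance ratio | Width ratio |
|---|---|---|---|---|
| 1 | 0.3 | −0.59 | 0.73 | 0.87 |
| 1 | 0.5 | −0.50 | 0.84 | 0.93 |
| 1 | 0.7 | −0.39 | 0.96 | 0.99 |
| 1 | 0.9 | −0.22 | 1.07 | 1.05 |
| 1.5 | 0.3 | −0.36 | 0.98 | 1.005 |
| 1.5 | 0.5 | −0.19 | 1.08 | 1.06 |
| 1.5 | 0.7 | 0.05 | 1.12 | 1.08 |
| 1.5 | 0.9 | 0.47 | 0.87 | 0.95 |

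**Scenarios, change from −5 min, equal SDs.** Here ρ = (r[−130, peak] − r[−130, −5])/√(2 − 2r[−5, peak]).

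| r[−130, peak] | r[−5, peak] | r[−130, −5] | ρ | Variance ratio | Width ratio |
|---|---|---|---|---|---|
| 0.5 | 0.7 | 0.7 | −0.26 | 1.05 | 1.04 |
| 0.7 | 0.9 | 0.9 | −0.45 | 0.90 | 0.96 |
| 0.7 | 0.9 | 0.7 | 0.00 | 1.125 | 1.08 |

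The interval widens in 4 of the first 8 cases and 2 of the last 3, so in 6 of 11. At SD 25 the adjusted half-width runs from 27.9 to 34.6 pg/ml. Even the best case exceeds the assumed difference of 20.

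**Worth of the extra planning figures.** Take the most favourable scenario, with residual SD 25 × √(1 − 0.59²) = 20.2. On 9 degrees of freedom its 95% interval is 13.9 to 36.9, which translates to 10 to 55 per group for a 20 pg/ml difference, allowing for the estimated slope. An observed ρ of −0.5 in 12 patients has an interval of −0.85 to 0.14. The unadjusted SD of 25 on 10 degrees of freedom is little worse placed: 17.5 to 43.9, or 14 to 77 per group. Neither could responsibly be used alone to cut the later sample size.

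**The case for a change.** The strongest case for adjustment is that it is cheap, valid and potentially useful. It needs one extra model on data already collected. In simulation at 6 per arm with normal data, ANCOVA held its type I error at 5.0%, against about 4.0% for the exact rank test. For the assumed 20 pg/ml difference its power was 22%, 24%, 28% and 38% at correlations of 0, 0.3, 0.5 and 0.7, against 20 to 21% for the rank test. Naming the model now would also fix the choice before unblinding.

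These figures are correct but do not make the plan deficient. Part of the power gap is the conservatism of an exact rank test at this size: an unadjusted t-test has 24% power, more than ANCOVA at zero correlation. The larger gains need correlations the documents do not support with any figure. A common-slope model would also be strained if suvorexant blunted the response in proportion to baseline. The data are kept, so an adjusted estimate can be computed later, and the promise of effect sizes does not exclude one.

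The baseline point partly stands. Two ORX draws precede the gas, and no rule says which one starts the change score. The two uses of baseline in Table 3 are weak evidence of conflict, because both attach to ratings and vital signs and not to the ORX draw. The two options answer different questions, but each compares randomised arms fairly. This is a detail left open, and does not show that the chosen analysis is wrong.

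**Conclusion.** The concern does not hold. An unadjusted rank-sum test on peak change is a sound choice for a 6-per-arm randomised pilot, and the planned summaries supply the inputs of the t-test calculation behind 25 per group. Adjustment for the −130 min value would change the 95% half-width from 32.2 to somewhere between 27.9 and 34.6 pg/ml, and would widen it in 6 of 11 scenarios. Its residual SD would be too imprecise to size the next study (10 to 55 per group). Reasonable statisticians could differ on whether to report it.

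This rests on the planning SD of 25 pg/ml, on approximately normal change scores with a common slope, and on assumed correlations and SD ratios. If |ρ| were known to be well above 0.37, adjustment would be worth more, but nothing in the documents establishes that. What remains is the unstated ORX baseline, a point of clarification that affects neither the validity of the test nor any stated figure.
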